### **5.5.6.3 Suicidality**

Upon administration of the Columbia-Suicide Severity Rating Scale (C-SSRS) assessments, each subject is evaluated for active suicidal ideation with specific plan and intent. Data collected from the C-SSRS assessments will be summarized by the scheduled visit for the safety sample reporting suicidality; suicidal behavior only, emergence of suicidal behavior; suicidal ideation only, emergence of suicidal ideation, emergence of serious suicidal ideation, and worsening of suicidal ideation.

Suicidality is defined as reporting any suicidal ideation or behavior. Suicidal behavior only is defined as reporting any type of suicidal behaviors (actual attempt, interrupted attempt, aborted attempt and preparatory acts or behavior) throughout assessment period. Emergence of suicidal behavior is defined as having no suicidal behavior at baseline and reporting any type of behavior at post-baseline. Suicidal ideation only is defined as reporting any type of suicidal ideation. Emergence of suicidal ideation is defined as having no suicidal ideation at baseline and reporting any type of ideation during treatment. Emergence of serious suicidal ideation is defined as having no suicidal ideation at baseline and reporting serious suicidal ideation with score of 4 or 5 on suicidal ideation severity rating during the treatment. At suicidal ideation severity rating assessment, each person is giving a score of 0 (no ideation present) to 5 (active ideation with plan and intent). Worsening of suicidal ideation is defined as having more severe in most severe suicidal ideation rating at post baseline than at baseline. Numbers of subjects reporting suicidal behavior will be reported by type of suicidal behavior.

Mean and mean change from baseline in suicidal ideation intensity total score for most severe ideation will be summarized by scheduled visit for the safety sample. The suicidal ideation intensity total score is sum of suicidal ideation severity rating scores for frequency, duration, controllability, deterrents and reasons for ideation. For each item, each subject gets the intensity score from 0 (none) to 5 (worst). Therefore, suicidal ideation intensity total score is range from 0 to 25. If the subject did not endorse any suicidal ideation, a score of 0 is given for the intensity scale.

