
Has subject engaged in Non-Suicidal Self-Injurious Behavior?
 
Interrupted Attempt: When the person is interrupted (by an outside circumstance) from starting the potentially self-injurious act (if not for that, actual attempt would have occurred). Overdose: Person has pills in hand but is stopped from ingesting. Once they ingest any pills, this becomes an attempt rather than an interrupted attempt. Shooting: Person has gun pointed toward self, gun is taken away by someone else, or is somehow prevented from pulling trigger. Once they pull the trigger, even if the gun fails to fire, it is an attempt. Jumping: Person is poised to jump, is grabbed and taken down from ledge. Hanging: Person has noose around neck but has not yet started to hang - is stopped from doing so. Has there been a time when you started to do something to end your life but someone or something stopped you before you actually did anything? If yes, describe:
	
Yes No  
 
Total # of interrupted _____

Aborted Attempt: When person begins to take steps toward making a suicide attempt, but stops themselves before they actually have engaged in any self-destructive behavior. Examples are similar to interrupted attempts, except that the individual stops him/herself, instead of being stopped by something else. Has there been a time when you started to do something to try to end your life but you stopped yourself before you actually did anything? If yes, describe:
	
Yes No  
 
Total # of aborted _____

Preparatory Acts or Behavior: Acts or preparation towards imminently making a suicide attempt. This can include anything beyond a verbalization or thought, such as assembling a specific method (e.g. buying pills, purchasing a gun) or preparing for one's death by suicide (e.g. giving things away, writing a suicide note). Have you taken any steps towards making a suicide attempt or preparing to kill yourself (such as collecting pills, getting a gun, giving valuables away or writing a suicide note)? If yes, describe:
	
Yes No  

Suicidal Behavior: Suicidal behavior was present during the assessment period?
	
Yes No  

Protocol 31-10-270

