
Controllability Could /can you stop thinking about killing yourself or wanting to die if you want to? (1) Easily able to control thoughts difficulty (2) Can control thoughts with little difficulty (3) Can control thoughts with some difficulty (4) Can control thoughts with a lot of (5) Unable to control thoughts (0) Does not attempt to control thoughts
	_____

Deterrents Are there things - anyone or anything (e.g. family, religion, pain of death) - that stopped you from wanting to die or acting on thoughts of committing suicide? (1) Deterrents definitely stopped you from attempting suicide you (2) Deterrents probably stopped you (3) Uncertain that deterrents stopped you (4) Deterrents most likely did not stop you (5) Deterrents definitely did not stop you (0) Does not apply
	_____

Reasons for Ideation What sort of reasons did you have for thinking about wanting to die or killing yourself? Was it to end the pain or stop the way you were feeling (in other words you couldn't go on living with this pain or how you were feeling) or was it to get attention, revenge or a reaction from others? Or both? (1) Completely to get attention, revenge or a reaction from others (2) Mostly to get attention, revenge or a reaction from others (3) Equally to get attention, revenge or a reaction from others and to end/stop the pain (4) Mostly to end or stop the pain (you couldn't go on living with the pain or how you were feeling) (5) Completely to end or stop the pain (you couldn't go on living with the pain or how you were feeling) (0) Does not apply
	_____

Protocol 31-10-270

SUICIDAL BEHAVIOR (Check all that apply, so long as these are separate events; must ask about all types)	Since Last Visit												

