
Completed Suicide:
	
 
 Yes	No	
 
 		
 
	Yes	No										
Yes	No												
													

Protocol 31-10-270

Answer for Actual Attempts Only		Most Lethal Attempt
Actual Lethality/Medical Damage: 0. No physical damage or very minor physical damage (e.g. surface scratches). 1. Minor physical damage (e.g. lethargic speech; first-degree burns; mild bleeding; sprains). 2. Moderate physical damage; medical attention needed (e.g. conscious but sleepy, somewhat responsive; second-degree burns; bleeding of major vessel). 3. Moderately severe physical damage; medical hospitalization and likely intensive care required (e.g. comatose with reflexes intact; third-degree burns less than 20% of body; extensive blood loss but can recover; major fractures). 4. Severe physical damage; medical hospitalization with intensive care required (e.g. comatose without reflexes; third-degree burns over 20% of body; extensive blood loss with unstable vital signs; major damage to a vital area). 5. Death	Date	
	Enter #	
Potential Lethality: Only Answer if Actual Lethality=0 Likely lethality of actual attempt if no medical damage (the following examples, while having no actual medical damage, had potential for very serious lethality: put gun in mouth and pulled the trigger but gun fails to fire so no medical damage; laying on train tracks with oncoming train but pulled away before run over). 0 = Behavior not likely to result in injury 1 = Behavior likely to result in injury but not likely to cause death 2 = Behavior likely to result in death despite available medical care	Date	
	Enter #	

Protocol 31-10-270

**Appendix 11 Visual Analog Scale (VAS) for Subject-reported Rating of Pain
at Most Recent Injection Site**

Date: _____ Time of Assessment: _____

Patient evaluation of pain at the most recent injection site via visual analog scale:

No pain |-----| Unbearably painful

Note: VAS is 100 mm line; current sample is not to scale

Adapted from Kane et al. Am J Psychiatry. 2003;160:1125-32.

Protocol 31-10-270

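### The SAP's definition of suicidal behavior omits the Completed Suicide item on the post-baseline C-SSRS form, so the C-SSRS tables can miss a suicide or show it as a non-fatal attempt

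*SAP*

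**What the plan says.** SAP section 5.5.6.3 sets out how the C-SSRS data are to be classified. The category it calls suicidal behavior only is met by "reporting any type of suicidal behaviors (actual attempt, interrupted attempt, aborted attempt and preparatory acts or behavior"). Nothing marks the list as a set of examples, and it is the only list of behavior types in the SAP.

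Three further rules use the notion of behavior without repeating the list:

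- The overall category: "Suicidality is defined as reporting any suicidal ideation or behavior".
- Emergence: "Emergence of suicidal behavior is defined as having no suicidal behavior at baseline and reporting any type of behavior at post-baseline".
- The count by type: "Numbers of subjects reporting suicidal behavior will be reported by type of suicidal behavior".

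SAP Appendix 4 plans CT-6.2.1 (incidence of suicidality) and CT-6.2.2 (incidence by type). It gives titles only, without shells.

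Protocol section 3.6.3.6 specifies the Baseline form at study entry and the Since Last Visit form afterwards. Both are in Protocol Appendix 10. The Suicidal Behavior block of the Since Last Visit form ends with a separate Yes/No entry, "Completed Suicide". The Baseline form has no such entry.

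**The concern.** The SAP's list matches the Baseline form, but the behavior rows after baseline are filled from the Since Last Visit form, which has one more item. The gravest outcome the scale can record therefore has no category in the analysis.

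The Synopsis of the protocol names suicide risk, as classified by the C-SSRS, as a safety endpoint, and Protocol section 3.5.1 says the scale serves to classify suicide events. If a suicide occurred, the C-SSRS behavior rows could show no behavior, or one unremarkable attempt, while the death listing showed a suicide. The SAP has no rule for reconciling the two.

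**Working it through.** No sample size, power or event-rate figure is involved, so the check is a comparison of items followed by a look at each way a suicide can be recorded.

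**Step 1. Items side by side** (Protocol Appendix 10 against SAP section 5.5.6.3)

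| Entry | Baseline form | Since Last Visit form | SAP list |
|---|---|---|---|
| Actual attempt | yes | yes | yes |
| Interrupted attempt | yes | yes | yes |
| Aborted attempt | yes | yes | yes |
| Preparatory acts or behavior | yes | yes | yes |
| Completed suicide | no | yes | no |
| Total | 4 | 5 | 4 |

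Both forms also carry an overall Yes/No question, "Suicidal behavior was present during the assessment period". The SAP does not use it to define behavior. Non-suicidal self-injury is left out of the count because it is not suicidal behavior.

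**Step 2. Must a suicide also be ticked as an actual attempt?** The block heading reads "Check all that apply, so long as these are separate events; must ask about all types". Taken literally, one fatal act is one event, so ticking Completed Suicide does not require a tick under Actual Attempt. The lethality scale, answered for actual attempts only, runs up to "major damage to a vital area). 5. Death", so the form also allows a fatal act to be entered as an attempt. Either entry is possible.

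**Step 3. What the SAP rule does with each entry**

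| How the suicide is recorded | Result under the stated definition |
|---|---|
| Completed Suicide only, no other behavior on study | Meets none of the four types; behavior count 0 instead of 1 |
| Completed Suicide only, with another behavior reported on study | Subject counted for the other behavior; the suicide has no category |
| Actual Attempt with lethality code 5 | Counted; not separable from a non-fatal attempt, as no C-SSRS lethality summary is planned |
| Both ticked | Counted as an attempt; no category shows the death |
| No form completed after the death | Absent from the C-SSRS tables under any definition |

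The first two rows assume that the four-type list also governs overall suicidality, emergence and the by-type count. That is the natural reading, because no other list exists, but the SAP attaches the list explicitly only to suicidal behavior only.

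**Step 4. Size of one case.** The SAP (section 4) anticipates about 500 to 800 subjects.

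- 1 / 500 = 0.20%
- 1 / 800 = 0.125%

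By-visit denominators are not in the documents.

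**Step 5. Where else a suicide would appear.** If reported as an adverse event, it appears in the listings CT-9.1 and CT-9.4 and, if treatment-emergent, in CT-8.2.6 and CT-8.4.1. Any completed C-SSRS form is listed in PDATA-17. None of these depends on the behavior definition.

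**The case against.** The strongest reply has four parts.

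- **A suicide fits the form's definition of an actual attempt**, and the lethality scale has a code for death, so a rater may well record it there, where the SAP list catches it. This is a fair account of one recording route, but the form does not require it. On that route the case is counted yet still cannot be told apart from an attempt the subject survived.
- **Completed Suicide can be read as an outcome rather than a fifth type.** It has no definition or probe question and follows the overall behavior item. That is arguable, but the entry sits in the Suicidal Behavior block, and calling it an outcome still leaves the outcome without a place in the C-SSRS summaries.
- **The wording for suicidality and emergence is broad enough to include a suicide.** This stands in part: the list is not repeated there, and without shells one cannot be sure how the tables will be programmed. Even so, the by-type count has no stated place for a suicide.
- **The outcome is reported elsewhere, and a death between visits may leave no C-SSRS form.** Both points stand. Adverse events are the primary measures in Protocol section 7.3, and C-SSRS summaries are among the secondary ones in section 7.4. This limits the point to the C-SSRS tables and explains why a new row needs a reconciling footnote.

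**Conclusion.** The concern holds. The SAP covers 4 of the 5 suicidal-behavior entries on the form used after baseline, and whichever way a suicide is recorded, no stated C-SSRS category identifies it.

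The worst case is a behavior count one subject too low per suicide. It requires that the suicide is recorded on a C-SSRS form, that only the separate item is ticked, that the subject reported no other behavior on study, and that the four-type list applies throughout. An undercount in the emergence row also requires no suicidal behavior at baseline. If the suicide is coded as a fatal attempt instead, the total is right and only the type is blurred.

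The discrepancy is small in number, and no formal analysis is affected, since the trial is descriptive. It should still be corrected, because it concerns the most serious outcome of a named safety endpoint and the rule is best settled without reference to the number of cases.

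**What to change.** In SAP section 5.5.6.3:

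- Add completed suicide to the behavior definition, and state that this definition applies to suicidality, suicidal behavior, emergence of suicidal behavior and the count by type.
- Show completed suicide as its own row in CT-6.2.1 and CT-6.2.2.
- State that an actual attempt with lethality code 5 goes into that row, and that a subject with both items ticked is counted once.
- Footnote any death coded as suicide that has no C-SSRS record, so that these tables agree with the death and adverse event outputs.

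The cost is one or two sentences, one extra row in each of two tables, and one footnote. The suicide item and the lethality code are already on the Since Last Visit form, so no new data are needed.

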3.6.3.6 Suicidality

Suicidality will be monitored using the C-SSRS at baseline, every subsequent monthly visit, and at Study Completion or the Early Termination visit. The C-SSRS was developed by a team of researchers at Columbia University to address the need for standardized classification of suicide reports to assess suicide risk. This scale consists of a baseline evaluation that assesses the lifetime experience of the subject with suicide events and suicidal ideation and a post-baseline evaluation that focuses on suicidality since the last study visit. A baseline C-SSRS will be completed and a C-SSRS Since Last Visit form will be completed at all designated visits. Copies of the C-SSRS forms are provided in [Appendix 10](#).

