Appendix 10 Suicide Severity Rating Scale (C-SSRS)

COLUMBIA-SUICIDE SEVERITY RATING SCALE (C-SSRS)

Baseline

Version 1/14/09

*Posner, K.; Brent, D.; Lucas, C.; Gould, M.; Stanley, B.; Brown, G.;
Fisher, P.; Zelazny, J.; Burke, A.; Oquendo, M.; Mann, J.*

Disclaimer:

This scale is intended for use by trained clinicians. The questions contained in the Columbia-Suicide Severity Rating Scale are suggested probes. Ultimately, the determination of the presence of suicidality depends on clinical judgment.

*Definitions of behavioral suicidal events in this scale are based on those used in **The Columbia Suicide History Form**, developed by [name] and [name], Conte Center for the Neuroscience of Mental Disorders (CCNMD), New York State Psychiatric Institute, [name]. (Oquendo M. A., Halberstam B. & Mann J. J., Risk factors for suicidal behavior: utility and limitations of research instruments. In M.B. First [Ed.] Standardized Evaluation in Clinical Practice, pp. 103 -130, 2003.)*

For reprints of the C-SSRS contact PPD New York State Psychiatric Institute, [name]; inquiries and training requirements contact PPD

Protocol 31-10-270

SUICIDAL IDEATION	

Ask questions 1 and 2. If both are negative, proceed to "Suicidal Behavior" section. If the answer to question 2 is "yes," ask questions 3, 4 and 5. If the answer to question 1 and/or 2 is "yes", complete "Intensity of Ideation" section below.
	
Lifetime: Time He/She Felt Most Suicidal

1. Wish to be Dead Subject endorses thoughts about a wish to be dead or not alive anymore, or wish to fall asleep and not wake up. Have you wished you were dead or wished you could go to sleep and not wake up?
 
If yes, describe:
	
Yes No  

2. Non-Specific Active Suicidal Thoughts General, non-specific thoughts of wanting to end one's life/commit suicide (e.g. "I've thought about killing myself") without thoughts of ways to kill oneself/associated methods, intent, or plan. Have you actually had any thoughts of killing yourself?
 
If yes, describe:
	
Yes No  

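### The C-SSRS category rules give no row that shows all serious ideation on treatment: a rise from score 1-3 to 4-5 is only 'worsening', and the baseline recall period is unstated.

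*SAP*

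**What the plan says.** SAP 5.5.6.3 sets out the C-SSRS summary categories on a severity rating that runs from 0 (none) to 5 (active ideation with plan and intent). The ideation rules are:

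- Emergence: "Emergence of suicidal ideation is defined as having no suicidal ideation at baseline and reporting any type of ideation during treatment".
- Emergence of serious ideation: "having no suicidal ideation at baseline and reporting serious suicidal ideation with score of 4 or 5".
- Worsening: "Worsening of suicidal ideation is defined as having more severe in most severe suicidal ideation rating at post baseline than at baseline".
- Ideation only: "Suicidal ideation only is defined as reporting any type of suicidal ideation".
- Suicidality: "Suicidality is defined as reporting any suicidal ideation or behavior".

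'Behavior only' is likewise defined as any of the listed behaviors, and emergence of behavior requires none at baseline.

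On the baseline itself, Protocol 3.6.3.6 describes the scale as having "a baseline evaluation that assesses the lifetime experience of the subject with suicide events and suicidal ideation", followed by a form covering the time since the last visit. The baseline form in Protocol Appendix 10 heads its ideation column "Lifetime: Time He/She Felt Most Suicidal". SAP 5.1.2 takes baseline as the last Trial 248 visit with data, and Protocol 7.2 takes the Week 52 visit of that trial. Neither says which C-SSRS form or recall period supplies the value.

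**The concern.** The only ideation row that names severity is closed to anyone with ideation at baseline, even at score 1. A move from passive or non-specific thoughts to intent or a plan during treatment is what a reader of this safety table most wants to see, and it is merged with small changes such as 1 to 2.

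The baseline definition adds a second difficulty. If it is a lifetime worst score, it acts as a ceiling: a serious episode that is new during this trial but no worse than the subject's worst ever is neither emergent nor worsening. The planned mean change in ideation intensity would then also set a lifetime-worst value against ratings that cover about a month.

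The 'only' labels are a smaller, separate matter. They tell the reader that the rows are mutually exclusive, and the definitions do not make them so.

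Suicide risk as classified by the C-SSRS is a named safety endpoint (Protocol synopsis, Criteria for Evaluation). It is rated monthly, in a trial whose secondary objective is long-term safety data.

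**Working it through.** The plan states no figure on this point, so there is none to reproduce. The check applies the SAP 5.5.6.3 rules literally to every pairing of a baseline score with a serious on-treatment score.

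**Inputs.** Baseline score 0 to 5 (6 values) and on-treatment score 4 or 5 (2 values): 6 × 2 = 12 pairings.

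| Baseline | On-treatment 4 | On-treatment 5 |
|---|---|---|
| 0 | emergent serious | emergent serious |
| 1, 2 or 3 | worsening, not emergent | worsening, not emergent |
| 4 | neither | worsening, not emergent |
| 5 | neither | neither |

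**Counts under the current rules.**

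- Emergent serious: 1 × 2 = 2 pairings. These also satisfy the worsening rule.
- Baseline ideation present: 12 − 2 = 10 pairings, none of which can be emergent serious.
- Of those 10, worsening takes 3 × 2 = 6 (from 1-3) plus 1 (4 to 5) = 7.
- In neither row: 10 − 7 = 3, namely 4 to 4, 5 to 4 and 5 to 5.
- All 12 count as 'ideation only' and as suicidality, without severity.

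**Does worsening reveal the serious cases?** Among baseline scores of 1 or more there are 10 possible rises: 4 + 3 + 2 + 1. Three of them (1 to 2, 1 to 3, 2 to 3) stay below 4, and the other 7 end at 4 or 5. All 10 fall in one row with no split, so the row total cannot be read as a count of serious ideation.

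**Does this depend on the recall period?** The gap for baseline 1-3 does not. The 3 pairings in neither row do. With a recent baseline they describe serious ideation already present at entry, and leaving them out of an emergence or worsening row is reasonable. With a lifetime baseline they can be new episodes during treatment.

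**Alternative rules.**

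- Emergent serious as baseline 0-3 to on-treatment 4-5: 4 × 2 = 8 of 12. It still omits 4 to 4, 4 to 5, 5 to 4 and 5 to 5.
- Any on-treatment 4-5, whatever the baseline: 12 of 12.

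**Labels.** A subject with any ideation and any behavior meets both 'only' definitions, so is reported in two 'only' rows. This needs no assumption.

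These are counts of possible score pairings, not shares of subjects. The documents give no distribution of baseline ideation, so no headcount follows.

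**The case against.** A reader might infer that serious ideation goes uncounted, and in the highest-risk subjects. The documents do not support that. Suicidality and 'ideation only' carry no baseline condition, so every on-treatment 4 or 5 is counted there. Worsening takes 7 of the 10 pairings barred from the serious row. Subject-level C-SSRS data are listed (PDATA-17), and suicide-related adverse events are tabulated (CT-8.2.6) and listed (CT-9.4). Exclusion 4 in Protocol Table 3.4.3-1 removes subjects whom the investigator judges to be at significant risk of suicide, so recorded past ideation cannot be equated with highest risk.

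The lifetime baseline is not settled either. Protocol 3.6.3.6 and Appendix 10 support it, but SAP 5.1.2 may already mean a recent rating from the last Trial 248 visit. The Trial 248 protocol, which might decide the matter, is not among the documents.

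Table CT-6.2.2, incidence of suicidality by type, might show ideation types 4 and 5. Its shell is not given, and the SAP text promises counts by type only for behavior, so it cannot be relied on.

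Finally, everything here is descriptive, no decision rests on these rows, and the 'only' definitions are written out, so no count is arithmetically wrong.

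Most of this stands as a limit on the claim. It does not supply a row that shows serious ideation on treatment. The adverse event outputs are an imperfect substitute: Protocol 5.2 elicits events with one general question, and I found no text requiring a C-SSRS 4 or 5 to be recorded as an adverse event.

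**Conclusion.** The point holds as a gap in presentation, not as lost data. Whatever baseline is used, a rise from 1-3 to 4-5 (6 of the 12 pairings) is reported only in rows without severity, and no row defined in the SAP text gathers all on-treatment scores of 4 or 5. If the lifetime form is the baseline, 3 further pairings (4 to 4, 5 to 4, 5 to 5) enter neither the emergent nor the worsening row. That part is conditional, and the missing statement of form and recall period is itself something to correct. The 'only' labels are misleading as they stand.

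How many subjects are affected cannot be derived from the documents. Any figure would rest on an assumed prevalence of baseline ideation, and would count subjects ineligible for a row, not events missed. The change should be made because suicide risk is a named safety endpoint and the remedy is close to free.

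**What to change.** In SAP 5.5.6.3 and the C-SSRS tables (CT-6.2.1 to CT-6.2.3):

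1. Define emergence of serious ideation as baseline 0-3 with any post-baseline 4 or 5, and keep 0 to 4-5 as a sub-row so that the present definition can still be read off.
2. Add a row for any on-treatment 4 or 5 irrespective of baseline, or a shift table of baseline score by worst on-treatment score. Item 1 alone does not cover baseline scores of 4 and 5.
3. Name the C-SSRS form and recall period used as baseline, and specify the recent, non-lifetime Trial 248 Week 52 rating for the emergence, worsening and change-from-baseline summaries. If no such rating was collected, say so and rely on the row or shift table in item 2.
4. Rename the two 'only' rows as any ideation and any behavior.

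The changes to rows and labels use ratings already scheduled for collection. The cost is SAP wording and a few extra table rows.
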